8.5. Esophageal Motility

- Measures LES resting pressure following standard protocol
- $> 50\%$ peristalsis with $> 30\%$ distal amplitudes
- 10 consecutive water swallows allows the assessment of propulsive motor function of the esophagus
- High-resolution motility is optional

9. Study Procedures

The schedule of observations and assessments to take place during the study follows on the next page. (**Table 4**)

Table 4. Study Events Schedule

	Initial Screening	Final Screening	Procedure	Post-Procedure/ Hospital Discharge	2-Week ±3 days	3-Month ± 15days	6-Month ± 20 days	12 and 24 Months ± 20 days
Inclusion/Exclusion Criteria	X	X						
Sign Informed Consent Form		X						
Demographics and Medical History	X							
Physical examination	X			X				
Record concomitant medications	X	X	X	X	X	X	X	
Recording of GERD Medications	X				X	X	X	X
Recording of duration of GERD Symptoms	X				X	X	X	X
Recording of type of GERD Symptoms	X				X	X	X	X
Recording of PPI Use; except for 2-week and 3-month visits, discontinue PPI usage for 7 days to evaluate study endpoints	X			X	X	X	X	X
RDQ, atypical symptom RSI, Quality of Life questionnaires GSRS, HRQL after being off PPI for at least 7 days	X						X	X
Discontinuation of anticoagulants if applicable (at least 10 days before scheduled TIF)	X							
EGD with optional biopsy		X					X	
Motility studies (High resolution optional)		X						
BRAVO pH study (at least 7 days after stopping all antisecretory compounds)		X					X	
Study Enrollment		X						
Hiatal Hernia Repair			X					
TIF 2.0 Procedure (if Hiatal Hernia successfully repaired with at least 2 cm of intra-abdominal esophagus)			X					
Adverse Event Reporting			X	X	X	X	X	

9.1. *Determination of Patient Eligibility – Screening Process*

Initial Screening -

The following pre-procedure data must be collected in order to determine patient eligibility:

- Demographics and medical history, to include age, weight, gender, and race
- Usage of GERD medication (medication, dosage, frequency and duration)
- Duration of GERD symptoms
- Type of GERD symptoms
- Duration of PPI Use
- Clinical symptom assessments (RDQ) and Quality of Life questionnaires (GSRS, HRQL, Atypical Symptom RSI)
- All general inclusion/exclusion criteria have been met

Upon completion of the Initial Screening Process, if it is determined that the patient does not have “troublesome” symptoms while on PPIs, they are **NOT eligible** for the study

Final Screening :-

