The following pre-procedure data must be collected in order to determine eligibility:

- Informed consent signing
- Physical Examination
- Days since last PPI intake (prior to BRAVO pH study)
- EGD with optional biopsy
- High resolution motility studies (optional)
- Upper GI endoscopy
- Bravo pH studies (48 hours)

Patients who have met all entry criteria are enrolled to the study.

9.2. *Prior to the Study Procedure*

- The usage of any anticoagulants will be discontinued before TIF for at least 10 days.
- 12-hours before the procedure, the patient is expected to be fasting.
- Immediately before the procedure, each patient will undergo an endoscopic examination of the stomach and esophagus.

9.3. *During the Study Procedure*

A Transoral Incisionless Fundoplication will be performed following the standard laparoscopic Hiatal Hernia Repair and closure of the diaphragmatic defect (crura closure will be made

posterior with 2-3 separate stitches). The patient will be terminated from the study if hiatal hernia cannot be repaired, with at least 2 cm intra-abdominal esophageal length.

TIF Procedure (Treatment)

The TIF procedure (treatment) will be conducted under continuous visualization following a standard TIF2.0 protocol (**Figures 8**).

[figure not shown]

Figure 8. Standard TIF2 protocol

The usage of any anticoagulants will be discontinued before HHR and TIF 2.0 for at least 10 days. Patients are expected to fast for 12 hours before the procedure. Antibiotic prophylaxis will be administered during induction of general anesthesia (oro-tracheal intubation and anti-emetic protocol; dehydrobenzoperidol, dexamethasone, Zofran, Primperan).

As stated in Section 10.2, immediately before the procedure, each patient will undergo an endoscopic examination of the stomach and esophagus. The EsophyX ZR will be inserted transorally through a bite-block into the esophagus with the patient in either in supine, or 45 degrees or left lateral position.

During a single insertion of the device, a valve similar to that created through antireflux surgery will be reconstructed by retraction of full-thickness plications and tailored placement of multiple fasteners circumferentially 1-3 cm above the Z-line. The procedure is expected to last for 30-45 minutes. The quality of the

created valve will be evaluated by an endoscopic examination immediately after the procedure. Any complications related to the procedure will be recorded.

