10.2.2 Effectiveness Analysis

The primary analysis timepoint for effectiveness is 6 months post TIF procedure. Descriptive summaries as described in 10.2.1 General Methodology will be provided for the primary effectiveness endpoint of proportion of patients with normalized esophageal acid exposure, and secondary endpoints of proportion of patients free of “troublesome” symptoms and proportion of patients with a clinically significant reduction in PPI consumption from their pre-TIF screening consumption.

At each assessment time point, RDQ, atypical symptom RSI, Quality of Life questionnaires GSRS, HRQL will summarized as continuous measures. At 6 months, changes from baseline will be similarly summarized for each of these instruments. As defined in Section 8.1, portions of patients with clinically significant improvements will also be reported with 95% confidence intervals for GERD-HRQL, GERD-GSRS, RSI, and RDQ.

In addition, for the primary endpoint, proportion of patients with normalized esophageal acid exposure, 44% was observed in the EGS RESPECT study. Non-inferiority testing will be conducted for the same proportion observed in the HEURISTIC study vs. the RESPECT result. The hypotheses are as follows.

H_0 : HEURISTIC 6-month normalization rate $\leq 44\% - 20\% = 24\%$

H_A : HEURISTIC 6-month normalization rate $> 44\% - 20\% = 24\%$

The HEURISTIC normalization rate will be considered non-inferior to the 44% RESPECT rate if H_0 can be rejected at a 1-sided $p < 0.05$ level by exact binomial

probability calculation. To achieve this goal in 50 evaluable patients, the observed 6-month normalization rate in HEURISTIC must be 18/50 (36%) or higher.

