Study Endpoints/Outcomes	Control	Pre-procedure Value	Post-procedure Value	Success Criteria
PRIMARY EFFECTIVENESS				
Normalized acid exposure	Self-Comparison	BRAVO Ph studies after off anti-secretory meds ≥ 7 days	BRAVO Ph studies at 6 months after off anti-secretory meds ≥ 7 days	Treatment success will be defined by a proportion of TIF patients with normalized acid exposure that is non-inferior to the RESPECT result as defined in 10.2.2.
SECONDARY EFFECTIVENESS				
GERD symptoms	Self-Comparison	Reflux Disease Questionnaire (RDQ) scores	Reflux Disease Questionnaire (RDQ) scores at and 6 months	Treatment success will be defined by a proportion of TIF patients free of troublesome symptoms at 6 months that is \geq the same proportion in RESPECT Trial (67%)
PPI usage	Self-Comparison	PPI usage (must be "daily")	PPI usage at 6 months	Treatment success will be defined by $\geq 50\%$ of TIF patients that has a clinically significant reduction, i.e. from "daily" PPI use to "none" or "occasional" use, at 6 months.

12. Risks

The following risks are anticipated and can result from the TIF procedure or general anesthesia:

Expected typical risks or discomfort:

- Pharyngolaryngeal pain (e.g., sore throat)
- Musculoskeletal pain (e.g., left shoulder pain)
- Temporary epigastric or abdominal pain, which can be treated with standard pain medication
- Temporary dysphagia (i.e., difficulty swallowing) due to swelling
- Nausea or vomiting

Unusual risks or discomfort:

- Oral or dental injury
- Bleeding
- Bloating sensation
- Hematoma

Rare risks:

- Esophageal perforation, laceration or tear
- Aspiration, hypoxia, achalasia

- Nerve damage
- Arrhythmia
- Pneumothorax, chest pain
- Pneumoabdomen
- Fistula
- Infection of the mediastinal space

Additional risks:

- Operation to remove a defective device or its parts
- Reoperation after a failed procedure (insufficient symptom relief)

13. Adverse Events

All adverse events will be monitored from the time of enrolling through the 6-month follow-up visit. Unanticipated adverse device effects (UADE) and SAEs will be monitored through the 12-month follow-up.

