15.2. *Device Accountability*

Device accountability records must be maintained at the study site. Each site will purchase the devices from EGS.

16. Ethical Considerations

16.1. *Declaration of Helsinki*

The Investigator will ensure that this study is conducted in full conformity with the current revision of the Declaration of Helsinki, and with the regulations and guidelines of FDA; whichever affords the greater protection to the patient.

16.2. *Institutional Review Board*

A copy of the protocol, proposed Informed Consent form, other written patient information and any proposed advertising material must be submitted to the IRB for written approval. A copy of the written IRB approval of the protocol and Informed Consent form must be received by EndoGastric Solutions before recruitment of patients into the study.

The Investigator must submit and, where necessary, obtain approval from the IRB for all subsequent protocol amendments and changes to the Informed Consent form. The Investigator should notify the IRB of deviations from the protocol or SAEs/UADEs occurring at the site and other SAE/UADE reports received from EndoGastric Solutions in accordance with local procedures.

The Investigator will be responsible for obtaining annual IRB approval and renewal throughout the duration of the study. Copies of the Investigator's reports and the IRB continuance of approval must be sent to EndoGastric Solutions.

16.3. *Informed Consent Form*

A sample Informed Consent form is provided in Appendix A for the Investigator to prepare for use at his/her site. The written Informed Consent documents should be prepared in the language(s) of the potential patient population.

The reviewing IRB and the sponsor must first approve the Informed Consent forms that are used. The Informed Consent forms that are used should be in accordance with the current guidelines as outlined by the Good Clinical Practices (GCP) guidelines, Declaration of Helsinki and the International Conference on Harmonization (ICH).

Prior to participation in the clinical trial, each patient must give written Informed Consent after the context of the study has been fully explained to the patient in language that is easily understood by the patient. The patients must also be given the opportunity to ask questions and have those questions answered to their satisfaction.

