last approval of marketing application or until at least 2 years have elapsed after last enrolled patient. These documents will be retained for a longer period of time by agreement with EndoGastric Solutions or in compliance with other regulatory requirements. When these documents no longer need to be maintained, it is EndoGastric Solutions responsibility to inform the Investigator. The Investigator will take measures to ensure that these essential documents are not accidentally damaged or destroyed. If for any reason the Investigator withdraws responsibility for maintaining these essential documents, custody must be transferred to an individual who will assume responsibility. EndoGastric Solutions must receive written notification of this custodial change.

17.3. *Criteria for Terminating Study*

EndoGastric Solutions reserves the right to terminate the study but intends only to exercise this right for valid scientific or administrative reasons and reasons related to protection of patients. Investigators and associated IRB will be notified in writing in the event of termination.

Possible reasons for study termination include (but are not limited to):

- The discovery of an unexpected, significant, or unacceptable risk to the patients enrolled in the study.

17.4. *Criteria for Suspending/Terminating a Study Center*

EndoGastric Solutions reserves the right to stop enrolling of patients at a study center at any time after the study initiation visit if no patients have been enrolled or if the center has multiple or severe protocol violations without justification or fails to follow remedial actions.

Possible reasons for suspending/terminating a study center include:

- Repeated failure to complete case report forms prior to scheduled monitoring visits.
- Failure to obtain written Informed Consent.
- Failure to report SAE/UADE to EndoGastric Solutions within 24 hours of knowledge.

17.5. *Investigator Responsibilities*

- Agree to sign and adhere to the Investigator Agreement
- Agree to participate in Investigator meetings as scheduled by EndoGastric Solutions
- Be willing to perform and be capable of performing treatment procedures as outlined in this protocol
- Comply with all required elements of this protocol Agree to obtain written Informed Consent before any study specific procedures are performed in accordance with GCP
- Complete all data modules prior to scheduled monitoring visits

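### Consent is scheduled after the off-PPI baseline questionnaires, against the protocol's own consent rules

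*Combined protocol and SAP*

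**What the plan says.** Section 9, Table 4 separates Initial Screening from Final Screening. The row "RDQ, atypical symptom RSI, Quality of Life questionnaires GSRS, HRQL after being off PPI for at least 7 days" is marked at Initial Screening, at 6 months, and at 12 and 24 months. It is not marked at Final Screening. The row "Sign Informed Consent Form" has one mark, at Final Screening.

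Section 9.1 gives the same order in prose. The Initial Screening list contains "Clinical symptom assessments (RDQ) and Quality of Life questionnaires (GSRS, HRQL, Atypical Symptom RSI" and no consent item. The first item of the Final Screening list is "Informed consent signing". Between the two lists stands an eligibility gate: a patient without troublesome symptoms on PPIs does not go further.

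The consent rules are elsewhere. Section 16.3 says "Prior to participation in the clinical trial, each patient must give written Informed Consent". Section 17.5 has the investigator "Agree to obtain written Informed Consent before any study specific procedures are performed in accordance with GCP". Section 16.4 requires exact adherence to the protocol and a written amendment for any change.

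On the use of the scores, 10.2.2 says "At 6 months, changes from baseline will be similarly summarized for each of these instruments". Table 5 gives "Reflux Disease Questionnaire (RDQ) scores" as the pre-procedure value for the symptom endpoint. Section 8.1 judges a 50% improvement in HRQL and GSRS totals against a baseline taken off PPIs.

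**The concern.** The scheduled order and the consent rules cannot both be followed. A site that keeps to Table 4 and 9.1 collects study questionnaires, and on Table 4's wording has patients interrupt a prescribed drug, before they have agreed to take part. A site that keeps to 17.5 must depart from the schedule, although 16.4 does not allow departures without an amendment.

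Two things are at stake. The first is patient protection: inclusion criterion 2 requires patients who depend on daily PPIs, and these are the patients asked to stop. The second is the standing of the baseline data. If the only pre-procedure scores were obtained before consent, their use in the change-from-baseline and responder summaries is open to challenge. The plan has no second baseline, and 10.1 rules out imputation.

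**Working it through.** The plan gives no figure on this point, so the check compares passages and counts schedule marks.

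**1. Placement**

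| Item | Table 4 | Section 9.1 |
|---|---|---|
| RDQ, RSI, GSRS, HRQL | Initial Screening; 6 months; 12 and 24 months | Initial Screening list |
| Consent signing | Final Screening only | Final Screening list |
| PPI state for the questionnaires | Off for at least 7 days | Not stated |

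The table and the prose agree on the order, so the point does not rest on one table cell that may have been misread.

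**2. Counts.** The questionnaire row is marked in 3 columns, and 1 of these is before the procedure. Consent is marked in 1 column. Pre-procedure questionnaire columns at or after the consent mark: 0 of 1. Instruments whose only scheduled baseline precedes consent: 4 of 4.

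**3. Are these study-specific procedures?** Section 9 presents Table 4 as the schedule of study assessments. The four instruments are named, reproduced in the appendices, tied to a drug-free state, and used as the analysis baseline in 8.1, 10.2.2 and Table 5. No passage describes the Initial Screening questionnaires as routine care, and none provides a waiver or an earlier consent.

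**4. When does the PPI stop begin?** On Table 4's wording it begins at least 7 days before the Initial Screening questionnaires. Even if both screening stages fell on one day, the stop would precede the signature by at least 7 days.

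**5. Evidence given little or no weight.** Table 4's separate PPI-use row also mentions a 7-day stop and is marked at Initial Screening. It is only supporting, because its mark is for recording use and its stop clause cannot apply to every marked visit: Hospital Discharge is marked, yet 9.4 continues PPIs for 14 days after the procedure. Table 4 gives no interval between the screening columns. Table 4 and 9.1 also differ on where the physical examination falls, but not on consent or the questionnaires. Figure 6 and the sample consent form were not available for this check.

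**6. Minor linked point.** Table 4 has the Initial Screening questionnaires done off PPI. Section 9.1 lists them without a PPI state, just before a gate on symptoms while on PPIs. The RDQ (Appendix E) asks about the last seven days. After at least 7 days off PPI, that recall window holds 7 − 7 = 0 on-PPI days. The text does not say whether this RDQ is meant to inform the gate. Inclusion criterion 3 can still be judged from history.

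**7. Reach.** The plan's only design calculation does not depend on consent timing. With success at 18 or more of 50, the exact binomial test has a one-sided error of 0.0384 at a true rate of 24% and a power of 0.9010 at 44%, which agrees with the stated 0.90.

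**The case against.** The strongest reply is that 17.5 covers only study-specific procedures and that Initial Screening may be ordinary work-up. The synopsis describes the 1- and 2-year quality-of-life follow-up as standard of care, and Table 4 puts those later questionnaires in the same row as the screening ones. That label, however, is given only to the later follow-up. Nothing extends it to a baseline collected in a required off-drug state and used in the analysis.

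A second reply is that the drug interruption rests on one row label. Section 9.1 is silent on PPI state at Initial Screening, and it lists days since last PPI intake only under Final Screening. This stands in part: the pre-consent PPI stop follows from Table 4 and not from 9.1. But Table 4 is explicit and 8.1 needs an off-PPI baseline, so silence in 9.1 does not remove the requirement. The pre-consent data collection holds whatever the PPI state.

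A third reply is that the affected endpoints are secondary or descriptive. This is correct and limits the point. The symptom success criterion in Table 5 compares a 6-month proportion with 67% from RESPECT, so the baseline RDQ does not enter that threshold. HRQL, GSRS and RSI are not named there as endpoints.

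Finally, the questionnaires could be moved to Final Screening instead. That would put the data after consent, but the 7 days off PPI would still come before a consent signed at that visit.

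**Conclusion.** The concern holds. Followed as written, the schedule breaches the protocol's own consent rules. This is a contradiction between passages, not a missing detail. The only scheduled baseline for all four questionnaires (4 of 4) precedes the single consent mark and, on Table 4's wording, comes after at least 7 days off PPI.

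The conclusion assumes that these questionnaires are study-specific, as their use in 8.1, 10.2.2 and Table 5 indicates, and that Initial Screening comes before Final Screening, as the gate in 9.1 requires. Neither the number of patients affected nor any effect on enrolment can be derived, because sites that follow 17.5 would consent first. The Bravo entry criterion, the primary endpoint measurement and the sample size are not directly affected. The change should be made. The PPI-state ambiguity in 9.1 is minor and adds no weight to this conclusion.

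**What to change.** Move the consent entry in Table 4, and the matching item in 9.1, to the start of Initial Screening, ahead of any study-driven PPI stop and any study questionnaire. Both places would then agree with 16.3 and 17.5. The off-PPI baseline that 8.1 needs stays as it is.

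As a minor addition, state in Table 4 and 9.1 the PPI state intended for each Initial Screening questionnaire, and say what documents inclusion criterion 3. The two passages must be reconciled. An RDQ completed before the PPI stop is one optional way to document the criterion.

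The cost is schedule wording in two places and consenting some patients who later fail screening. The optional RDQ would add one short questionnaire. Sample size, power and the analyses do not change.

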7.1. Selection Criteria

The table on the following pages outlines the specific inclusion and exclusion criteria for the study. Before randomization in the study, a patient must meet all of the inclusion and exclusion criteria.

Inclusion Criteria:	
1.	Age 18-80years
2.	Dependent upon daily PPIs for > 6 months. Daily use is defined as a double dose, or full dose or half dose taken daily for more than 80 % of the total number of days during the proceeding evaluation period
3.	Troublesome symptoms, specifically heartburn or regurgitation, while on optimized dose of PPI's. Troublesome heartburn or regurgitation symptoms are those which occur a minimum of 2 days a week and are mild to severe in severity.
4.	Abnormal ambulatory (Bravo) pH study after off PPI therapy for 7 days, i.e. >5.3% of the time with pH < 4 in a 48-hour monitoring period
5.	Normal or near normal esophageal motility (by Upper GI/ esophagram or manometry as required)
6.	Pre-enrollment Hiatal Hernia (axial height and transverse dimension) from > 2cm and up to 4 cm inclusive
7.	Patient willing to cooperate with post-procedure dietary recommendations and assessment tests at the requisite follow-up visits
8.	Signed informed consent
Pre-enrollment Exclusion Criteria:	
1.	BMI > 35
2.	Hiatal hernia \leq 2 and > 4 cm
3.	Esophagitis Los Angeles grade C or D
4.	Esophageal ulcer
5.	Esophageal stricture
6.	Long-segment Barretts esophagus (Prague: C > 1, M > 3)
7.	Esophageal motility disorder
8.	Pregnancy or plans for pregnancy in the next 12 months (in females)
9.	Immunosuppression
10.	ASA > 2
11.	Portal hypertension and/or varices
12.	History of previous resective gastric or esophageal surgery, cervical spine fusion, Zenker's diverticulum, esophageal epiphrenic diverticulum, achalasia, scleroderma or dermatomyositis, eosinophilic esophagitis, or cirrhosis
13.	Active gastro-duodenal ulcer disease
14.	Gastric outlet obstruction or stenosis
15.	Severe gastroparesis or delayed gastric emptying confirmed by solid-phase gastric emptying study if patient complains of postprandial satiety during assessment
16.	Coagulation disorders
17.	Symptoms including gas bloat and dysphagia.
18.	Any other presenting condition that in the opinion of the investigator would not make participation in this study in the patients best interest.
Post-enrollment Exclusion Criteria:	
1.	Inability to repair Hiatal hernia with at least 2cm of intra-abdominal esophagus length.

7.2. *Withdrawal*

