11. Does regurgitation change your diet?	 0  1  2  3  4  5
12. Does regurgitation wake you from sleep?	 0  1  2  3  4  5
13. Do you have difficulty swallowing?	 0  1  2  3  4  5
14. Do you have pain with swallowing?	 0  1  2  3  4  5
15. If you take medication, does this affect your daily life?	 0  1  2  3  4  5
16. How satisfied are you with your present condition?	 0  1  2  3  4  5

Satisfied Neutral Dissatisfied

Appendix E – Reflux Disease Questionnaire**Reflux Disease Questionnaire**Please answer each question by ticking one box per row.**1. Thinking about your symptoms over the last seven days, how often did you have the following?**

	Did not have	Less than one day a week	One day a week	2-3 days a week	4-6 days a week	Daily
a. A burning feeling behind your breastbone						
b. Pain behind your breastbone						
c. A burning feeling in the centre of the upper stomach						
d. A pain in the centre of the upper stomach						
e. An acid taste in your mouth						
f. Unpleasant movement of material upwards from the stomach						

2. Thinking about symptoms over the last seven days, how would you rate the following?

	Did not have	Very mild	Mild	Moderate	Moderately severe	Severe
a. A burning feeling behind your breastbone						
b. Pain behind your breastbone						
c. A burning feeling in the centre of the upper stomach						
d. A pain in the centre of the upper stomach						

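### Table 4 and section 9.1 put the off-PPI questionnaires at Initial Screening but consent at Final Screening, contrary to sections 16.3 and 17.5

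*Combined protocol and SAP*

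**What the plan says.** **Timing of the questionnaires.** The Table 4 row reads "RDQ, atypical symptom RSI, Quality of Life questionnaires GSRS, HRQL after being off PPI for at least 7 days". Before the procedure it is marked at Initial Screening only. Section 9.1 agrees on the visit. Its Initial Screening list opens with "The following pre-procedure data must be collected in order to determine patient eligibility" and includes "Clinical symptom assessments (RDQ) and Quality of Life questionnaires (GSRS, HRQL, Atypical Symptom RSI".

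**Timing of consent.** Table 4 marks the consent row at Final Screening only. In section 9.1, "Informed consent signing" is the first item under Final Screening and does not appear under Initial Screening.

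**Consent rules.** Section 16.3 requires written consent before a patient takes part in the trial. Section 17.5 requires it before any study-specific procedure. Section 16.4 says the protocol must be followed exactly and changed only by written amendment.

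**Eligibility on PPI.** Inclusion criterion 3 (section 7.1) requires heartburn or regurgitation on an optimized PPI dose, with this threshold: "Troublesome heartburn or regurgitation symptoms are those which occur a minimum of 2 days a week and are mild to severe in severity". Section 9.1 applies the test at the end of Initial Screening. A patient is not eligible "if it is determined that the patient does not have “troublesome” symptoms while on PPIs". The RDQ in Appendix E asks: "Thinking about your symptoms over the last seven days, how often did you have the following".

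**Use of the off-PPI scores.** Section 8.1 judges later improvement in GERD-HRQL and GSRS against an off-PPI baseline. The number of days off PPI is recorded at Final Screening: "Days since last PPI intake (prior to BRAVO pH study".

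**The concern.** Inclusion criterion 2 makes every candidate a daily PPI user. An instruction to stop that drug for at least a week so that study questionnaires can be scored is a change in treatment made for research. On the written schedule it happens before the patient has agreed to anything. A site cannot satisfy both Table 4 and section 17.5: either the stop comes before consent, or the site departs from the schedule. Section 17.4 lists failure to obtain written consent among the reasons for suspending a centre, so sites are exposed as well as patients.

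The second issue is about evidence. Section 9.1 names the RDQ among the data that determine eligibility, and the eligibility test is about symptoms on PPI. The scheduled RDQ is taken in the opposite drug state.

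**Working it through.** **The plan's own figure.** The primary rule is at least 18 normalized patients out of 50, tested against 24% with power at 44% (sections 10.2.2 and Sample Size and Power Estimation). Exact binomial:

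- P(X ≥ 18 | n = 50, p = 0.24) = 0.0384, below 0.05
- P(X ≥ 17 | n = 50, p = 0.24) = 0.0718, above 0.05, so 18 is the correct cutoff
- P(X ≥ 18 | n = 50, p = 0.44) = 0.9010, which reproduces the stated 0.90

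None of these inputs depends on when consent is signed or when the questionnaires are given.

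**Order of events.**

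| Item | Table 4 | Section 9.1 |
|---|---|---|
| RDQ, RSI, GSRS, HRQL | Initial Screening, at least 7 days off PPI | Initial Screening, drug state not stated |
| Consent signing | Final Screening | Final Screening |
| Days since last PPI intake | no separate row | Final Screening |

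The table and the text give the same order independently, so a misread table does not explain it. The 7-day stop is needed before the questionnaires, the questionnaires belong to Initial Screening, and consent belongs to the later stage. The stop and all four questionnaires therefore come before the signature.

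**Could Initial Screening be routine care?** The synopsis uses standard-of-care wording only for the 1- and 2-year quality-of-life follow-up. The baseline scores serve the study: section 8.1 uses GERD-HRQL and GSRS to define response, and Table 5 names pre-procedure RDQ scores for the symptom endpoint.

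**Recall windows.** Largest possible number of on-PPI days in the window = max(0, recall days − days off PPI), with 7 days off:

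- RDQ (Appendix E, 7 days): max(0, 7 − 7) = 0 of 7
- GSRS (Appendix C, 2 weeks): 14 − 7 = at most 7 of 14
- GERD-HRQL (Appendix D, 2 weeks): 14 − 7 = at most 7 of 14
- RSI (Appendix F, 1 month, taken as 30 days): 30 − 7 = at most 23 of 30

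For any stop of 7 days or more the RDQ stays at 0. GSRS and GERD-HRQL mix the two drug states. An RDQ completed on PPI before the stop would cover 7 of 7 on-PPI days.

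**What else supports criterion 3.** Table 4 marks an inclusion/exclusion check at both screening stages. Section 9.1 requires the general criteria to be met at Initial Screening. Criterion 3 itself carries the on-PPI, frequency and severity terms. The same list collects medical history, type and duration of symptoms, and GERD medication with dose and frequency.

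**The case against.** **On consent.** Sections 16.3 and 17.5 already state the rule that protects patients, and a site that obtains consent early satisfies both. The off-PPI condition sits in a row label shared with the 6-, 12- and 24-month visits. The Initial Screening text in section 9.1 orders no PPI stop, and days since last intake are recorded only at Final Screening. This may be loose drafting rather than an intended stop before consent. That is plausible, and it makes the repair easy, but it does not remove the conflict. Section 16.4 does not leave sites free to choose their own order, and even without the stop, section 9.1 places the four study questionnaires before consent.

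**On criterion 3.** A reader might infer that the schedule leaves the criterion unverifiable, or that patients well controlled on PPI would be enrolled because they relapse when it is stopped. The documents do not support that. The criterion names no instrument, section 9.1 does not say the RDQ decides the matter, and the criteria check is scheduled at both stages. The off-PPI questionnaires also have a proper purpose as an outcome baseline. What stands is narrower: this RDQ, listed as eligibility data, cannot supply the on-PPI evidence.

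**On consequences.** A reader might also infer bias in the comparison with the 67% RESPECT symptom rate, or two separate PPI stops for each patient. Neither is shown. The documents give no frequency of misclassified patients and no spacing between the two screening stages.

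**Conclusion.** The consent sequence is wrong as written and should be corrected. Followed literally, all 50 planned patients would stop PPI for at least 7 days and complete four questionnaires before signing. Screen failures would add to that number. This assumes that sites apply the Table 4 row label at Initial Screening.

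The RDQ point is secondary. The scheduled form covers 0 of 7 on-PPI days and cannot itself support criterion 3, which then rests on the investigator's check and history. That is a gap in documentation. It does not show that ineligible patients would enter.

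The primary endpoint, sample size, 18/50 rule and power are unaffected, and no effect on the secondary comparisons is shown.

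**What to change.** 1. In Table 4 and section 9.1, move consent signing to Initial Screening, before any study-ordered PPI stop.
2. Move the off-PPI RDQ, RSI, GSRS and HRQL to Final Screening, within the BRAVO washout and before capsule placement. This keeps the off-PPI baseline that section 8.1 needs. The days-off-PPI entry already made at that stage then documents the drug state for both, and one stop serves both.
3. Preferably, add one RDQ at Initial Screening on the optimized PPI dose, used only to document criterion 3. State in advance which of its six symptom items count as heartburn or regurgitation.

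The cost is a protocol amendment with IRB approval and, for step 3, one short form (six symptoms rated for frequency and severity, 6 × 2 = 12 rows) per screened patient. Sample size, primary endpoint and primary analysis do not change.
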